11.4 Response Criteria using FDG-PET scans (for MIBG non-avid patients)

This section included as a reference only and will NOT be used in NANT 2011-01 as all patients must be MIBG avid

Patients known to be non-avid for MIBG should have FDG-PET scans performed for monitoring response. FDG-PET avid lesions will be scored by the presence or absence of a lesion that is two times above background.

11.4.1 Complete response (CR)

Resolution of all FDG-PET uptake in all FDG-PET avid lesions identified at baseline and no new FDG-PET avid lesions.

11.4.2 Partial response (PR)

Reduction of number of lesions by FDG-PET by $\geq 50\%$. No new FDG-PET avid lesions.

11.4.3 Stable disease (SD)

Changes that do not meet the criteria for PR or PD.

11.4.4 Progressive disease (PD)

New lesions on FDG-PET scan. Note: biopsy may be done to exclude causes of FDG-PET uptake other than tumor. If biopsy is negative for tumor (neuroblastoma and/or ganglioneuroblastoma), patient will not meet definition of PD.

11.4.5 Not evaluable (NE)

FDG-PET scan of inadequate quality to evaluate response or if based on Study Management Committee/PI review it is deemed that there is insufficient data to grade response.

11.4.6 Not involved (NI)

No FDG-PET uptake that is two times above background

11.4.7 Not Done (ND)

FDG-PET scan not done at that timepoint.

On central review, FDG-PET avid lesions will be evaluated by both the Curie scoring method and by enumeration of lesions to grade response.

11.5 Urine Catecholamines

Due to variance with diet and concomitant medications, frequently missing dopamine levels, and lack of standardized methodology for this assay, urine catecholamines will not be utilized in grading response. Results of urine catecholamines will still be requested at all response evaluation time points and recorded in database as both actual and as “elevated” or “not elevated”. Catecholamines must be at least 3 standard deviations above the mean for age to be classified as elevated.

11.6 Definition of Overall Response for Each Patient

The criteria below will be used to define the overall response for each patient, with consideration of all three individual response parameters: CT/MRI, MIBG (FDG-PET if tumor is not MIBG avid), and Bone Marrow.

11.6.1 Complete Response (CR)

Response of CR or NI for MIBG (FDG-PET if tumor is not MIBG avid), CT/MRI and bone marrow.

11.6.2 Complete Response-MRD (CR-MRD)

Response of CR or NI for MIBG (FDG-PET if MIBG non-avid), CT/MRI response of CR or NI, with BM response of CR-MRD.

11.6.3 Partial Response (PR)

Response of PR in both CT/MRI and MIBG (FDG-PET scan if tumor is not MIBG avid); or response of PR in either CT/MRI or MIBG (FDG-PET if MIBG non-avid) with response of CR, NI, or SD-NTL for other parameter or response of CR for MIBG with SD-NTL for CT response. Bone marrow response of either CR, CR-MRD, NI, or SD for patients with maximum amount of tumor $\leq 5\%$ at that given time point.

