10.3 Response Evaluation

10.3.1 Definition of Evaluable for Response

All patients who are registered onto the study must be assessed for response to treatment, even if there are major protocol treatment deviations or if they are ineligible. Each patient will be assigned one of the following categories (see Section 11):

- a. Complete response
- b. Complete response-Minimal Residual Disease (MRD)
- c. Partial response
- d. Stable disease
- e. Minor response
- f. Progressive disease
- g. Early death from malignant disease
- h. Early death from toxicity
- i. Early death because of other cause
- j. Inevaluable (not assessable, insufficient data, patients off therapy early due to toxicity)
- k. Never received any of the study drugs: ¹³¹I-MIBG, vorinostat, vincristine, or irinotecan.

All eligible, randomized patients will be included in the intent-to-treat analysis of response, according to the randomization outcome. Patients in groups a through c will be classified as responders; patients in groups d through k will be classified as non-responders. In a second analysis, the proportion of responders (patients in groups a through c) will be calculated from the subset of patients who are evaluable for response (as defined in the next paragraph).

In the secondary analysis (per protocol), patients will be considered evaluable for response if they receive ¹³¹I-MIBG that is at least 85% of their prescribed dose (or at least 85% of 1200 mCi protocol maximum dose for patients whose calculated dose exceeds 1200 mCi) plus at least 80% of any prescribed systemic agents (at least 4 days of irinotecan or at least 11 days of vorinostat), or withdraw early due to tumor progression, clinical progression/deterioration, or toxicity. In addition, patients who do not withdraw early must meet the criteria to be adequately evaluated for each of the 3 disease parameters (if they had disease at baseline for that parameter) as described in Section 11, in order to be considered evaluable for response. For each patient not evaluable for response, an additional patient will be enrolled to meet the accrual goals in Section 10.5.

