If a solitary soft tissue lesion extends into both the chest and abdomen/pelvic regions, score 3 for that lesion. For example, a large paraspinal mass that extends along the thoracic and lumbar spine would be scored a 3 for Region 10. Any corresponding metastatic bone disease within the thoracic or lumbar spine would be scored separately for the cervico-thoracic spine (Region 2) and lumbar spine (Region 4).

Conjugate planar imaging will be used to score a given region. SPECT scans may be used as an adjunct, but only to help delineate the location of the MIBG avid lesion.

The **relative score** is calculated by dividing the absolute score at each time by the corresponding pre-treatment overall score. The relative score of each patient is calculated at each response assessment and classified as below:

- a. Complete response: all lesions of uptake on MIBG scan completely resolved.
- b. Partial response: Relative score ≥ 0.1 to ≤ 0.5
- c. Stable disease: Relative score > 0.5 to < 1.2
- d. Progressive disease: New lesions on MIBG scan OR a relative score ≥ 1.2 . Biopsy of new lesions may be done to rule out progressive disease. If biopsy is negative for tumor (neuroblastoma and/or ganglioneuroblastoma), patient will not meet definition of PD.
- e. Not evaluable: MIBG scan of inadequate quality as assessed by central reviewer.
- f. Not involved: No MIBG avid lesions at study entry and subsequent response time points.
- g. Not done: MIBG scan not done at a given response time point.

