11.6.6 Minor response (MR)

Complete response, Complete-MRD response, and/or partial response for one parameter (i.e. CT/MRI, MIBG (FDG-PET if MIBG non-avid), bone marrow), with response of stable disease for second parameter and any response other than PD or inevaluable for third parameter.

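### With marrow stable at 5% tumor or less, CT CR plus MIBG CR counts as non-response while CT CR plus MIBG PR counts as response; the summary table also conflicts with the text

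*Combined protocol and SAP*

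**What the plan says.** Section 10.1 selects the arm with the highest observed response rate on central review after one course, and section 11.0 has central review apply the section 11 criteria. Section 10.3.1 makes the split: "Patients in groups a through c will be classified as responders; patients in groups d through k will be classified as non-responders". Groups a to c are CR, CR-MRD and PR; Minor response is group e.

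The overall categories are defined in section 11.6:

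- **CR (11.6.1):** "Response of CR or NI for MIBG (FDG-PET if tumor is not MIBG avid), CT/MRI and bone marrow".
- **CR-MRD (11.6.2):** MIBG CR or NI, "CT/MRI response of CR or NI, with BM response of CR-MRD".
- **PR (11.6.3):** There are three imaging routes. The first is PR on both imaging parameters. The second is "response of PR in either CT/MRI or MIBG (FDG-PET if MIBG non-avid) with response of CR, NI, or SD-NTL for other parameter". The third, which is the only one that does not need an imaging PR, is "response of CR for MIBG with SD-NTL for CT response". Marrow may be CR, CR-MRD, NI, or SD with no more than 5% tumor "at that given time point".
- **Minor response (11.6.6):** CR, CR-MRD or PR on one parameter, "with response of stable disease for second parameter and any response other than PD or inevaluable for third parameter".

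Section 11.3 sets the MIBG categories from the Curie relative score. CR needs all uptake resolved; the next category is "Partial response: Relative score ≥ 0.1 to ≤ 0.5".

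The table in 11.6.10 is offered as a summary of these definitions. Its PR row for MIBG PR lists CT CR, PR or SD-NTL, but not CT NI. It has no PR row for MIBG CR with CT SD-NTL. It dates the 5% marrow limit to study entry in the CT PR row and leaves it undated in the MIBG PR row. Its CR-MRD row accepts CT SD-NTL, which 11.6.2 does not.

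**The concern.** A response scale should not take responder status away from a patient whose disease clears further. This one does so for a patient with CT and MIBG both clear and a small stable marrow residue. No reason is stated, and 11.6.3 accepts MIBG CR with the same marrow when non-target CT lesions remain, so it looks like an omission.

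Separately, a grader working from the table and one working from the text can reach different answers for the same patient. One such state follows directly from the protocol's rules. MIBG uptake in bone alone is eligible (3.2.5), intramedullary bone lesions are not followed on CT/MRI even when active (11.1.3), and a patient with no target or non-target lesions is CT NI (11.1.4.6). With MIBG PR, that patient is a responder by the text but not by the table. Section 2.2 reports that, in the large single-agent phase 2 trial, patients with disease confined to bone/bone marrow or to soft tissue were more likely to respond.

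Selection turns on observed counts. One patient regraded moves an arm's rate by 1/35 = 2.9 points at the final analysis, or 1/27 = 3.7 points at about 27 per arm at the second interim.

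**Working it through.** The plan gives no figure to reproduce, so the rules were coded and applied to every combination of states. MIBG NI is left out because eligibility requires uptake; PD and not-evaluable states are also left out. No order of precedence is stated, so categories were applied in the order CR, CR-MRD, PR, SD, Minor response. PR must come before Minor response: otherwise the 11.6.3 allowance for stable marrow at 5% or less would never operate.

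**1. The inversion, with marrow SD at 5% or less at the time point**

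| CT | MIBG | CR? | CR-MRD? | PR by text? | Result | Responder |
|---|---|---|---|---|---|---|
| CR | PR | no | no | yes | PR | yes |
| CR | CR | no: marrow is SD | no: marrow is not CR-MRD | no: no imaging PR, and CT is not SD-NTL | Minor response | no |
| PR | CR | no | no | yes | PR | yes |
| NI | PR | no | no | yes | PR | yes |
| NI | CR | no | no | no | Minor response | no |

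The table in 11.6.10 gives the same results for the first two lines, so letting either source govern does not remove the defect. For CT NI the inversion exists in the text only, because the table does not list CT NI with MIBG PR as PR.

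**2. How many states are inverted.** 5 CT states (CR, PR, SD, SD-NTL, NI) x 3 MIBG states (CR, PR, SD) x 5 marrow states (CR, CR-MRD, NI, SD at 5% or less, SD above 5%) = 75. Under the text, 2 are inverted: CT CR or CT NI, with MIBG CR and marrow SD at 5% or less. Only the CT CR state is inverted in both text and table.

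**3. Text against table.** Splitting marrow SD by 5% at entry and 5% at the time point gives 3 + (2 x 2) = 7 marrow states, and 5 x 3 x 7 = 105 combinations.

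| Undated limit read as | Responder by text only | Responder by table only | Total discordant |
|---|---|---|---|
| response time point | 10 | 2 | 12 |
| study entry | 13 | 4 | 17 |

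- Under both readings, 5 of the text-only cells are CT NI with MIBG PR. Three of these (marrow CR, CR-MRD or NI) fit no table row. The other two (marrow SD at 5% or less now, split by entry level) are Minor response in the table.
- Four more are CT SD-NTL with MIBG CR. Two of these (marrow CR or NI) fit no table row unless SD-NTL is counted as SD, which gives Minor response.
- The table-only cells have marrow SD at 5% or less at entry and above 5% at the time point.
- CT SD-NTL with MIBG CR and marrow CR-MRD is PR by text and CR-MRD by table, a responder either way.

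**4. The MIBG gap.** The maximum Curie score is 10 regions x 3 = 30. A ratio above 0 and below 0.1 occurs when a baseline of 11 to 30 falls to 1 (20 pairs; 1/11 = 0.091) or a baseline of 21 to 30 falls to 2 (10 pairs; 2/21 = 0.095). A fall to 3 cannot qualify, since 3/30 = 0.1. Total: 20 + 10 = 30 pairs with no category.

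**5. Effect of the proposed PR wording.** It changes 2 of the 75 text states, the two inverted ones, from Minor response to PR, and no others.

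**The case against.** The inversion itself could not be rebutted. The best counter-arguments concern its weight.

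*The table is only a summary, so the text already governs.* This has force where the table merely has no matching row. But for CT NI, MIBG PR and stable marrow at 5% or less, the text gives PR and the table's own Minor response row applies, which is a direct contradiction. The dating of the 5% limit is another. Neither place states an order of precedence.

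*The MIBG gap adds little.* This stands as a matter of emphasis. Under the text, reading the gap as CR or as PR alters responder status only at CT CR or CT NI with marrow SD at 5% or less, which are the states already inverted. The 30 pairs measure a labelling gap, not 30 changes of outcome.

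*No effect on the ranking is shown.* This also stands. All arms use the same criteria, and randomization balances on marrow involvement. Nothing in the documents gives the frequency of these states or a difference by arm. That limits the severity; it does not make the rule coherent.

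*The fix is not purely additive.* Correct if grading has been done from the table: the 2 (or 4) table-only cells would lose responder status.

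**Conclusion.** The concern holds and should be fixed. As written, the primary endpoint grades one deeper response as non-response in 2 of 75 states by the text, one of which the table shares. Text and table give different responder status in 12 or 17 of 105 states. Amendment 7A revised these criteria to clarify the marrow and overall response definitions (2.7.4), yet the conflicts remain.

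The conclusion assumes that PR takes precedence over Minor response. The cell counts give equal weight to states that will not be equally common, and they say nothing about how many patients are affected or whether the selected arm would change. Two smaller points are editorial: 10.3.2 cites criteria v1.1 while section 11 is v1.2, and its list of site-reported responses sent for central review leaves out Minor response.

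**What to change.** **Wording**

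- In 11.6.3, define PR as: MIBG CR, PR or NI; CT/MRI CR, PR, NI or SD-NTL; at least one of the two CR or PR; marrow CR, CR-MRD, NI, or SD with 5% tumor or less at that time point; applied when CR and CR-MRD are not met.
- In 11.3, define MIBG PR as a relative score above 0 and up to 0.5 with residual uptake.
- In 11.6.10, add CT NI to the MIBG PR row, add a PR row for MIBG CR with CT SD-NTL, date the 5% limit to the time point throughout, and match the CR-MRD row to 11.6.2. State that the text governs and that PR is assessed before Minor response.
- In 10.3.2, correct the version number and add Minor response to the central review list.

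**Process**

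Settle the rule before finalising any central review that feeds a selection decision (10.1.1). The people who decide should have no access to response results by arm. Section 3.1 sends each arm assignment to the study chair, vice-chair and committee members, so name the decision-makers. State in advance which version drives selection, apply it to every patient, and report response rates by arm under both the as-written and the corrected rule.

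**Cost**

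This is a late clarification of the primary endpoint, after first-interim results went to the DSMB. Against the 11.6.3 text it can only add responders; against the table it can also remove some. That is why the blinding and the double report are needed. Otherwise it takes protocol wording and a small re-derivation, mostly from data already collected. Some marrow slides may have to be requested, because section 13.0 routinely asks for follow-up slides only where the site reports marrow CR or CR-MRD.

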11.6.10 Summary

The overall response as assessed at any particular time point based on consideration of each of the three parameters as defined above is summarized in the following table:

Overall Response Assignment			
CT/MRI Response	MIBG Response	Bone Marrow Response	Overall Response
PD for any one parameter with any response (including Not Done or Inevaluable) for the other 2 parameters. PD may also be defined by clinical assessment of the treating physician only.			PD
CR	CR	CR	CR
CR for one parameter with either CR or NI for other parameters			CR
MIBG response= CR or NI CT/MRI response = CR or SD-No Target Lesions or NI		CR-MRD	CR-MRD
CR or PR or SD-No Target Lesions	PR	CR or CR-MRD or NI -OR- SD if $\leq 5\%$ tumor in bone marrow	PR
PR	CR or PR or NI	CR or CR-MRD or NI -OR- SD if $\leq 5\%$ tumor in bone marrow at study entry	PR
SD for one parameter, with SD or NI or SD-NL for other two parameters			SD
CR or CR-MRD or PR for at least one parameter, SD for a second parameter, and any response other than PD or Not Evaluable for other parameter			Minor Response
Response of Not Evaluable for any one of the 3 parameters that had measurable/evaluable tumor at study enrollment and no PD for any parameter.			Not Evaluable
No response evaluations performed for any of the 3 parameters			Not Done
NI or non-target lesions only at enrollment and no PD on subsequent timepoint	NI at enrollment and no PD at subsequent time point	NI at enrollment and no PD at subsequent time point	No Progression

*For patients who utilize FDG-PET in place of MIBG response, then substitute FDG-PET response for MIBG response in this table to define overall response.

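### Section 11.6 grades complete MIBG and CT/MRI clearance with at most 5% residual marrow tumor as Minor Response (non-responder), but the same patient with only partial MIBG clearance as PR (responder)

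*Combined protocol and SAP*

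**What the plan says.** The primary endpoint is centrally reviewed objective response after one course (10.3.2). CR, CR-MRD and PR count as response, and "patients in groups d through k will be classified as non-responders" (10.3.1); Minor Response is group e.

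Section 11.6 sets the overall grades:

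- **CR (11.6.1):** "Response of CR or NI for MIBG (FDG-PET if tumor is not MIBG avid), CT/MRI and bone marrow".
- **CR-MRD (11.6.2):** MIBG CR or NI, "CT/MRI response of CR or NI, with BM response of CR-MRD".
- **PR (11.6.3):** three imaging routes. The first is "Response of PR in both CT/MRI and MIBG". The second is "response of PR in either CT/MRI or MIBG (FDG-PET if MIBG non-avid) with response of CR, NI, or SD-NTL for other parameter". The third is "response of CR for MIBG with SD-NTL for CT response". Under any route, marrow may be CR, CR-MRD, NI, or SD with no more than 5% tumor at that time point.
- **SD (11.6.5):** SD in at least one parameter, and only SD, NI or SD-NTL in the rest.
- **Minor Response (11.6.6):** "Complete response, Complete-MRD response, and/or partial response for one parameter", SD in a second, and anything except PD or inevaluable in the third. The 11.6.10 table has the same rule: "CR or CR-MRD or PR for at least one parameter, SD for a second parameter".

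The table has two PR rows. One takes CT/MRI CR, PR or SD-NTL with MIBG PR; its 5% marrow limit carries no time point. The other takes CT/MRI PR with MIBG CR, PR or NI, and sets the 5% limit at study entry.

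**The concern.** A response grade used as a binary endpoint should never fall when one component improves and the others stay the same. Here it can. If MIBG improves from PR to CR, with CT/MRI CR and marrow SD at no more than 5%, the patient changes from responder to non-responder.

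The trial selects the arm with the highest observed response rate and requires no minimum margin (10.1). Response counts also feed the rule for dropping an arm (Appendix VIII, A.2.2) and the stochastic curtailment rule (10.1.1). Individual gradings can therefore matter, and the patients affected are those with marrow involvement whose imaging has cleared completely.

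**Working it through.** This is a question of classification, so the plan has no figure to reproduce.

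**The key patient: MIBG CR, CT/MRI CR, marrow SD with at most 5% tumor.**

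- CR fails because marrow must be CR or NI.
- CR-MRD fails because marrow must be CR-MRD.
- PR fails. Neither imaging parameter is PR, which closes the first two routes, and CT/MRI is not SD-NTL, which closes the third.
- SD fails because a CR parameter is not allowed.
- Minor Response is met, and it is the only category met. The table gives the same result.

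**The comparator: the same patient with MIBG PR.** The second PR route is met in the text, and the MIBG-PR row is met in the table. This patient also literally satisfies the Minor Response wording, and no order of precedence is stated. PR has to prevail, because otherwise the clause allowing marrow SD up to 5% would have no effect.

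**All relevant combinations, marrow SD with at most 5% at the assessment, PR taking precedence:**

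| CT/MRI | MIBG | Text | Table |
|---|---|---|---|
| CR | PR | PR | PR |
| CR | CR | Minor | Minor |
| NI | PR | PR | Minor |
| NI | CR | Minor | Minor |
| SD-NTL | PR | PR | PR |
| SD-NTL | CR | PR | Minor |
| PR | PR | PR | PR |
| PR | CR | PR | PR only if marrow was at most 5% at study entry |

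The reversal is in both text and table for CT/MRI CR, in the text only for NI, and in the table only for SD-NTL. The text also reverses across CT/MRI results: MIBG CR with CT/MRI SD-NTL is PR, but MIBG CR with CT/MRI CR or NI is Minor Response.

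**Example.** CT/MRI is CR and marrow falls from 20% to 2%. Marrow is SD, since section 11.2 has no marrow PR. A Curie score falling from 12 to 6 gives a relative score of 6/12 = 0.5, which is MIBG PR (11.3), so the overall grade is PR. A fall from 12 to 0 is MIBG CR, so the overall grade is Minor Response. This takes the undated limit in the table's MIBG-PR row as applying at the assessment, as 11.6.3 does. The reversal does not depend on that reading: a patient at or below 5% both at entry and at restaging, with tumor still seen, meets the limit either way.

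**Weight of one patient.** 1/35 = 2.9 percentage points at the final analysis, about 1/27 = 3.7 at the second interim and about 1/20 = 5 at the first.

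**How close the top two arms may be.** Exact binomial calculation, three arms of 35, no arm dropped and no early stop. The true rates are assumed. The probability that the top two arms are tied or one responder apart is:

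- 45% at 20/20/20%
- 30% at 20/20/30%
- 19% at 20/20/35% (the 15-point difference in 10.5)

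This shows how sensitive selection is to a single grading. It does not estimate how often this rule would change the winner.

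**The case against.** The strongest reply is that the gap is narrow. It needs all MIBG uptake resolved, CT/MRI at CR, and a little morphologic marrow tumor remaining, all after one course. Nothing in the documents shows that this is common or that it differs between arms. That stands, and it limits the severity.

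Three stronger readings are tempting, and the documents do not support them.

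- A reader might infer that text and table reverse together whatever the CT/MRI result. They do so only for CT/MRI CR. For NI the table has no PR row for MIBG PR, so it grades both patients as Minor Response. For SD-NTL the text grades both as PR.
- A reader might infer that the rule works against the better radiosensitizer. No section links this pattern to an arm.
- A reader might infer that regrading needs no further material. Section 10.3.2 sends institutional CR, CR-MRD, PR and SD to central review and does not list Minor Response. Section 13.0 requires restaging marrow slides only where marrow CR or CR-MRD is reported, and these patients have marrow SD.

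Timing also counts. The first interim results went to the DSMB in March 2017 (10.1.1), so any change to grading now follows a look at the data and has to be handled openly.

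None of this removes the reversal for CT/MRI CR. Precedence cannot rescue that patient, who meets no other category. Nor can central review, which must apply the same criteria (11.0).

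**Conclusion.** The point holds for the rule as written. With marrow SD at no more than 5% and CT/MRI CR, moving from MIBG PR to MIBG CR turns a responder into a non-responder in both text and table. The same reversal appears for CT/MRI NI in the text only and for SD-NTL in the table only. The primary endpoint is therefore not monotone in tumor response.

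The conclusion rests on two readings: that PR prevails where PR and Minor Response are both met, and that the components are graded as section 11 defines them. Each affected patient moves an arm of 35 by 2.9 points. How many there would be, and whether selection would change, cannot be calculated from the documents. A reader might infer that the selected arm is unreliable; that would need the frequency of the pattern by arm, which is not given. The rule should be fixed, but the documents do not show that it undermines the trial.

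**What to change.** 1. Add to 11.6.3: MIBG CR with CT/MRI CR or NI, and bone marrow SD with at most 5% tumor at that time point, is PR. Limiting this to marrow SD keeps it from overlapping CR and CR-MRD.
2. State in 11.6.6 that PR takes precedence over Minor Response.
3. Make the 11.6.10 PR rows match the text: add MIBG CR with CT/MRI CR or NI (marrow SD at most 5%), MIBG CR with CT/MRI SD-NTL, and CT/MRI NI with MIBG PR. Use one time point for the 5% limit throughout. The table also admits CT/MRI SD-NTL under CR-MRD where 11.6.2 does not; align these too, although both grades are responses.
4. Apply the rule to all patients at central grading, including those already graded, blind to arm. Add institutional Minor Responses with this pattern to the central-review list in 10.3.2.
5. Report the primary analysis under the grading as now written as a sensitivity analysis, and disclose that the clarification followed the first interim analysis.

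The cost is small: a few lines of text and table, re-derivation from recorded component grades, and central review of the affected patients, possibly with retrieval of existing marrow slides. No new patient assessments are needed.
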